4.8.2 Immunogenicity analyses

Dupilumab anti-drug antibody (ADA) status (negative or titer value, if positive in the ADA assay) at Visit 2 (Day 1), Week 12, Week 24/EOT and follow up at Week 36 will be provided. The neutralizing antibody status for ADA positive samples will be provided.

Incidence will be provided for the following ADA response categories:

Pre-existing immunoreactivity is defined as:

An ADA positive response in the assay at baseline with all post first dose ADA results negative, OR an ADA positive response at baseline with all post first dose ADA responses less than 4-fold over baseline titer levels.

Treatment-emergent ADA responses are defined as:

A positive response in the ADA assay post first dose, when baseline results are negative or missing.

Treatment-emergent ADA responses are further classified as Persistent, Indeterminate or Transient

- a) Persistent Response- Defined as a treatment-emergent ADA response with two or more consecutive ADA positive sampling time points, separated by greater than ($>$) 12-week period (84 days), with no ADA negative samples in between.
- b) Indeterminate Response- Defined as a treatment-emergent response with only the last collected sample positive in the ADA assay.
- c) Transient Response- Defined as a treatment-emergent response that is not considered persistent OR indeterminate.

Treatment-boosted response is defined as:

An ADA positive response in the assay post first dose that is greater-than or equal to 4-fold over baseline titer levels, when baseline results are positive.

Titer values (Titer value category)

- Low (Titer <1000)
- Moderate ($1,000 \leq \text{Titer} \leq 10,000$)
- High (Titer $>10,000$)

On-treatment ADA incidence will also be derived in the same way except that only on-treatment measurements (measurements during the treatment epoch) are considered post first dose.

The following summary will be provided based on ADA population for the on-treatment period and during the study:

- Number (%) of participants with pre-existing immunoreactivity
- Number (%) of participants with treatment-emergent ADA
- The summary statistics (including number, median, Q1, Q3, minimum and maximum) of the peak post-baseline titer for participants with treatment-emergent ADA, and participants with persistent, indeterminate and transient ADA response
- Number (%) of participant with transient treatment-emergent ADA
- Number (%) of participants with persistent treatment-emergent ADA
- Number (%) of participants with indeterminate treatment-emergent ADA
- Number (%) of participants with treatment-boosted ADA
- The summary statistics (including number, median, Q1, Q3, minimum and maximum) of the peak post-baseline titer for participants with treatment-boosted ADA
- The summary statistics (including number, mean, SD, median, Q1, Q3, minimum and maximum) of the ratio of peak post-baseline titer to baseline titer for participants with treatment-boosted ADA
- Listing of ADA peak titer levels and neutralizing antibody status
- Number (%) of participants with neutralizing antibody status

Analysis of treatment-emergent ADA response

Number (%) of participants with treatment-emergent ADA positive response at each visit will be summarized by each intervention group.

Plot of percentage of participants with treatment-emergent ADA positive response at each visit will be provided by each intervention group.

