### 1.3 SCHEDULE OF ACTIVITIES (SOA)

Procedures	Screening (2 to 4 weeks before Day 1)	Intervention period (Weeks)			Follow-up (12 weeks)	Notes
		0 (Day 1)	12	24		
Visit	1	2 a	3	4 (EOT) b	5 (EOS)	
Screening/baseline:						
Informed consent	X					
Medical history	X					
Prior and concomitant medication	X	X	X	X	X	Concomitant medication including rescue OCS taken since last visit will be collected throughout the study
Demographics	X					
Inclusion/exclusion criteria	X	X				
Patient e-diary training	X	X				
Randomization		X				
Study intervention						
Call IVRS/IWRS	X	X	X	X	X	
IMP administration			X c			IMP will be administered every other week except (for study A and study C) for children <30 kg and ≥15 kg where it will be administered every 4 weeks. The planned last dose is at Week 22 except (for study A and study C) for children <30 kg and ≥15 kg where it will be administered at Week 20. Participants (or their care givers) are allowed to perform IMP injections at home.
Dispense/Upload electronic diary d	X		X			Device is dispensed at Screening (including instructions for use). At the EOS, the e-diary is returned to the site.
Safetye						
Physical examination f	X	X		X	X	
Vital signs g	X	X	X	X	X	
Electrocardiogram (12 lead)	X			X		ECG to be locally collected and read

Procedures	Screening (2 to 4 weeks before Day 1)	Intervention period (Weeks)			Follow-up (12 weeks)	Notes
		0 (Day 1)	12	24		
Visit	1	2 a	3	4 (EOT) b	5 (EOS)	
Hematology, biochemistry, urine analysis h	X	X	X	X	X	
Hepatitis, HIV Serology, TB test i	X					
Pregnancy test j	Serum	Ur	Ur	Ur	Ur	In between visit urine pregnancy tests must be performed at home (Weeks 4, 8, 16, 20, 28, and 32)
AE reporting, including SAEs	X	X	X	X	X	
Pharmacokinetics and ADAe						
Serum PK samples for dupilumab concentration k		X	X	X	X	
Anti-dupilumab antibody k		X	X	X	X	
Biomarkerse						
Serum total IgE		X	X	X	X	
Basophil activation test (optional sub-study)		X	X	X		For participants (except pediatric participants in Studies A and B and all Study C participants) who decide to participate and provide consent for the optional basophil activation test.

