4 STATISTICAL ANALYSES

4.1 GENERAL CONSIDERATIONS

This SAP provides a comprehensive and detailed description of strategy and statistical techniques for the summary and analysis of EFC16461 Study C (omalizumab naïve) only. Study A (omalizumab naïve) and Study B (omalizumab intolerant or incomplete responders) were summarized separately in different SAPs.

In general, continuous data will be summarized using the number of observations available, mean, standard deviation (SD), median, minimum, and maximum. Categorical and ordinal data will be summarized using the count and percentage of participants.

The baseline value of efficacy parameters is defined as the last available value up to randomization date and prior to the first dose of study medication unless otherwise specified. The baseline value of the other parameters is defined as the last available value prior to the first dose of investigational medicinal product (IMP) if the participant is treated, or the last available value up to randomization date if the participant is not exposed to IMP.

Observation period

The observation period will be divided into 4 segments:

- The **pre-treatment period** is defined as the period up to first IMP administration.
- The **treatment-emergent (TE) period** is defined as the period from the first IMP administration to the last IMP administration + 98 days. The treatment-emergent period includes the following 2 periods:
 - The **on-treatment period** is defined as the period from the first IMP administration to the last administration of the IMP + 14 days (+28 days for children <30 kg)
 - The **residual treatment period** is defined as the period from the end of the on-treatment period to the end of the treatment-emergent period.
- The **post-treatment period** is defined as the period from the end of the treatment-emergent period.

The on-study observation period is defined as the time from start of intervention until the end of the study defined as the status date collected on e-CRF page “Completion of End of Study”.

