For the pharmacokinetics/pharmacodynamics variables summary, the reference date for the derivation of relative days of measurements will be the date of first IMP administration if the participant is treated with study intervention, or the randomization date if the participant is not treated. Pharmacokinetics /pharmacodynamics variables will be summarized by the analysis window defined in [Table 12](#) for the by visit descriptive analyses. All available values of measurements will be assigned to the appropriate visit window. In the event of multiple measurements of the same test in the same window, the one closest to the targeted visit date will be used for the by-visit summary. If they are at the same number of days away from the target day, the latest one will be used. For procedures planned on Visit 2, if it is done on the same date as the first IMP injection but the performance time is missing, it will belong to Visit 2 time window.

Table 12 - Time window for pharmacokinetics/pharmacodynamics variables

| Visit | Target Day | Serum dupilumab, ADA, Total IgE | Skin biopsy (substudy) | Basophil activation (substudy) |
|-------------------|------------|---------------------------------|------------------------|--------------------------------|
| Visit 1 | -28 to -14 | | | |
| Visit 2 (Week 0) | 1 | <1- | <1- | <1- |
| Visit 3 (Week 12) | 85 | 1+-126 | | 1+-126 |
| Visit 4 (Week 24) | 169 | 127-210 | >1+ | >126 |
| Visit 5 (Week 36) | 253 | >210 | | |

1-: up to 1st dose date/time or randomization if participant is not treated; 1+: after 1st dose date/time or randomization date if participant is not treated;

Unscheduled visits

Unscheduled visit measurements of laboratory data, vital signs and ECG will be used for computation of baseline, the last on-treatment value, analysis according to PCSAs, and the shift summaries for safety. They will also be included in the by-visit summaries if they are re-allocated to scheduled visits. Unscheduled visit measurements for efficacy data will be included in the by-visit summaries if they are re-allocated to scheduled visits.

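### Persistent ADA in Study C needs positives more than 84 days apart, but planned samples are exactly 84 days apart, so on schedule two consecutive positive visits are classed as transient

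*SAP*

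**What the plan says.** Study C SAP 4.8.2 sorts treatment-emergent ADA responses into three classes.

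- *Persistent* needs at least two consecutive positive sampling points, "separated by greater than ($>$) 12-week period (84 days), with no ADA negative samples in between".
- *Indeterminate* is "a treatment-emergent response with only the last collected sample positive in the ADA assay".
- *Transient* is everything else.

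The same section says ADA status "at Visit 2 (Day 1), Week 12, Week 24/EOT and follow up at Week 36 will be provided". Table 12 in section 5.4 sets the post-dose target days at 85, 169 and 253. Its Week 24 row reads "Visit 4 (Week 24) | 169 | 127-210 | >1+ | >126", so the ADA window for that visit is Days 127 to 210. When several samples share a window, "the one closest to the targeted visit date will be used for the by-visit summary".

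The Study C SAP also asks for an on-treatment version of every ADA summary, including the persistent count, in which "only on-treatment measurements (measurements during the treatment epoch) are considered post first dose". It does not define the treatment epoch. Section 4.1 defines an on-treatment period as "the period from the first IMP administration to the last administration of the IMP + 14 days (+28 days for children <30 kg". The protocol's Schedule of Activities states: "The planned last dose is at Week 22 except (for study A and study C) for children <30 kg", for whom it is Week 20.

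The Study A and Study B SAPs carry the same persistent rule but not the on-treatment derivation.

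**The concern.** The threshold equals the planned spacing of the visits, and the rule demands that it be exceeded. A participant who attends on schedule and is positive at two visits in a row therefore cannot be persistent on those two results. The ordering of the classes becomes odd: positive at Week 36 alone is indeterminate, while positive at Weeks 24 and 36 with no later negative is transient, although the second is the stronger evidence of persistence. The on-treatment table has only two planned post-dose samples, so it contains a row that on-schedule data cannot fill.

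The SAP also does not say whether separation runs from first to last positive or between neighbours, or whether it uses nominal or actual days.

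At stake are the persistent and transient counts, the peak-titre summaries by class, the concentration plots if persistence is one of the ADA variables plotted, and the optional explorations of ADA against efficacy and safety.

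**Working it through.** **Inputs.** The threshold is 12 × 7 = 84 days, to be exceeded (Study C SAP 4.8.2); this reproduces the plan's figure. Target days are 1 + 7 × week: 1 + 84 = 85, 1 + 168 = 169 and 1 + 252 = 253, matching Table 12. A treatment-emergent response requires a negative or missing baseline, so the Day 1 sample cannot be one of the positives.

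**Step 1, gaps on target days.** 169 − 85 = 84; 253 − 169 = 84; 253 − 85 = 168. Neither neighbouring gap exceeds 84.

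**Step 2, classes on target days**, measuring first to last positive of a run.

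| Weeks 12, 24, 36 | Present rule (> 84) | With ≥ 84 |
|---|---|---|
| +, +, − | transient | persistent |
| −, +, + | transient | persistent |
| +, +, + | persistent (168 days) | persistent |
| +, −, + | transient | transient |
| +, −, − or −, +, − | transient | transient |
| −, −, + | indeterminate | indeterminate |

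If every neighbouring gap had to exceed 84 days, even +, +, + would fail. With Weeks 12 and 24 only: +, + is transient; +, − is transient; −, + is indeterminate. No on-treatment pattern is persistent.

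**Step 3, actual dates.** Let the Week 12 and Week 24 samples be a and b days off target, so gap = 84 + b − a. The tolerance is an assumption: Protocol 4.1 allows ±3 days on the length of the treatment and post-treatment periods, and 7.1.1 gives a ±3-day window for participants who stopped treatment, but no window is given for the on-treatment Week 12 visit. With a and b each from −3 to +3, equally weighted, there are 49 pairs and gaps run from 78 to 90:

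- gap > 84: 21 pairs (43%), persistent;
- gap = 84: 7 pairs (14%), transient;
- gap < 84: 21 pairs (43%), transient.

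Transient: (7 + 21)/49 = 28/49 = 57%. For any gap distribution symmetric about 84 days the share is (1 + P(gap = 84))/2, hence at least 50%; here (1 + 7/49)/2 = 57%. If gaps run only long (uniform 84 to 90) it is 1/7 = 14%; if only short (78 to 84), 7/7 = 100%. The range over these assumptions is 14% to 100%.

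**Step 4, on-treatment summary, same ±3 days.**

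- *The epoch keeps late Week 24 samples:* 21/49 = 43% of pairs are persistent.
- *The epoch is the 4.1 on-treatment period, with the last dose exactly on schedule:* every-2-week dosing ends at Week 22, Day 155, and 155 + 14 = 169; every-4-week dosing ends at Week 20, Day 141, and 141 + 28 = 169. The Week 24 sample is in period for 7 × 4 = 28 pairs. Of these the gap exceeds 84 in 3 + 2 + 1 + 0 = 6. So 6/49 = 12% are persistent, (28 − 6)/49 = 22/49 = 45% transient, and in 21/49 = 43% the Week 24 sample falls outside the period. The dosing interval itself has a ±3-day tolerance (Protocol Table 3), so a late last dose would move the end past Day 169.

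In the out-of-period case, a participant positive at both visits has one on-treatment sample and becomes indeterminate; one positive only at Week 24 drops out of the on-treatment treatment-emergent count.

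**Step 5, checking a replacement.** Changing > to ≥ still misses gaps of 78 to 83 days (21/49 pairs). A minimum of 84 − 3 − 3 = 78 days admits all 49. A minimum is still needed: if the Day 169 sample is missed, an early end-of-treatment sample on Day 130 falls in the Week 24 window, and 130 − 85 = 45 days.

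**The case against.** **Samples rarely fall exactly on target.** This is correct, and a reader might infer from the on-schedule result that the on-treatment persistent row will be empty. The documents do not support that: with ordinary scatter, or an extra event-driven sample, some gaps exceed 84 days. What remains is that the class then depends on visit-day scatter rather than on the antibody response.

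**The strict threshold may be deliberate.** A reader might say that the rule contradicts its own reference to two or more samples. It does not: count and separation are joint conditions, and two positives 85 days apart meet both. A reader might also infer that nobody in the study can be persistent; three positives in a row span 168 days and qualify on a first-to-last reading. But if three positives were intended, the on-treatment row has no purpose, and the SAP does not state which reading applies.

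**Inclusive counting gives 85 days.** The SAP states no such convention, and separation reads as a plain difference.

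**Any day cut-off leaves edge cases.** This stands in part. Samples on Days 95 and 169 are 74 days apart and would stay transient under a 78-day minimum. The gain is that the cut-off no longer sits on the planned interval.

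**Materiality and comparability.** The sub-classes are descriptive, and Studies A and B use the same wording. Both points stand and limit the severity.

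**Conclusion.** The concern holds as a minor defect. On target days, every participant positive at exactly two consecutive visits is transient, and no on-treatment pattern is persistent. With an assumed ±3 days at both visits, 57% of date pairs remain transient. On-treatment, 43% or 12% of pairs are persistent, depending on how the treatment epoch is read; the 12% also assumes an on-schedule last dose. The documents give no ADA incidence, so the number of participants affected cannot be stated.

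A reader might infer that the protocol's ADA endpoint is compromised. The threshold rule does not reach it: treatment-emergent incidence, the indeterminate count and the ADA-positive/negative grouping do not use the 84-day condition, and no efficacy test depends on it. The undefined treatment epoch is a separate gap. If it excludes late Week 24 samples, it can change on-treatment treatment-emergent and indeterminate counts as well.

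**What to change.** Before database lock, replace definition (a) in Study C SAP 4.8.2 with wording to this effect:

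*Persistent: a treatment-emergent ADA response with two or more consecutive collected ADA-positive samples assigned to scheduled visits and uninterrupted by any negative sample, where the first and last of those visits are nominally at least 12 weeks apart and their actual sampling dates are at least 78 days apart.*

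State that 78 days is 12 weeks less an assumed ±3 days at each visit. State also that a missed visit does not break the run, so positive at Week 12, missed at Week 24 and positive at Week 36 stays persistent (168 days on target). The indeterminate and transient wording can stay.

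Define the treatment epoch so that the scheduled Week 24/end-of-treatment sample is included within its visit tolerance.

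Report the present more-than-84-day version alongside, for comparison with Studies A and B.

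The cost is one extra derivation and a definition that differs from the other two studies; no new data are needed. The persistent count will usually stay the same or rise, but not always: an event-driven positive that is not the sample assigned to a scheduled visit would no longer count as one of the two.

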4.8.2.1 Association of Immunogenicity with Exposure, Safety and Efficacy

The safety and efficacy analysis mentioned below will be conducted using the following categories:

ADA positive participants: Participants with treatment-emergent or treatment-boosted response.

ADA negative participants: Participants with pre-existing immunoreactivity or negative in the ADA assay at all time points.

Impact of ADA on PK profile

Potential associations between ADA variables (eg, ADA peak titers, neutralizing antibody status, treatment-emergent, persistent, indeterminate and transient response, treatment-boosted) and impact on serum concentration profile of dupilumab may be explored. Plot of concentration of functional dupilumab in serum versus visit will be provided by ADA variables for each dupilumab dose group. Individual participant plots of dupilumab concentration according to ADA status will be provided.

Impact of ADA on clinical efficacy endpoints

Associations between the ADA variables (eg, ADA peak titers, neutralizing antibody status, treatment-emergent, persistent, treatment-boosted) and the primary efficacy endpoint may be explored for the dupilumab dosed group.

Association of ADA with clinical safety endpoints

Association of safety versus ADA status may be analyzed in the ADA population. The safety assessment may focus on the following events:

- Severe injection site reactions last longer than 24 hours or serious injection site reactions,
- Hypersensitivity reactions (SMQ (20000214) hypersensitivity narrow search confirmed by medical review),
- Anaphylactic reactions (SMQ (20000021) anaphylactic reaction narrow search).

Associations between ADA variables (eg, ADA peak titers, neutralizing antibody status, treatment-emergent, persistent and treatment-boosted) and safety may be explored.

4.8.3 Pharmacodynamic/genomics endpoints

Venous blood samples will be collected at Visit 2 (Week 0), Visit 3 (Week 12), Visit 4 (Week 24/EOT), and Visit 5 (Week 36), for measurement of total IgE in serum. Total IgE will be measured using validated quantitative methods.

For those participants (with exception of adolescents and children) who consent to the optional pharmacogenetic/pharmacogenomic sample collection section of the ICF, serum/plasma for archival samples for possible future analysis of potential biomarkers of drug response, disease activity, safety, and the Type 2 inflammation pathway, and blood samples for exploratory genetic analysis of DNA or RNA will be collected and stored for possible future use. Participation is optional. Participants who do not wish to participate in the genetic research may still participate in the study.

For those participants (with exception of adolescent and children) who consent to the optional basophil activation (substudy), samples will be taken at Visit 2, Visit 3 (Week 12) and Visit 4 (Week 24/EOT).

For those participants (with exception of adolescent and children) who consent to the optional skin biopsy (substudy), the sample will be taken from lesion and non-lesion skin using punch biopsy at Visit 2 and Visit 4 (Week 24/EOT).

Total IgE will be summarized in the safety population defined as participants who actually received at least 1 dose or part of a dose of the IMP. Baseline values will be the last value collected prior to the first IMP. Descriptive statistics (including number, mean, SD, median, Q1, Q3, min, max) of biomarkers at baseline will be summarized.

Summary plots (median +/- interquartile range) on values at each visit, absolute changes from baseline and percent changes from baseline will be provided for the total IgE by intervention group and visit.

Exploratory analysis of DNA/RNA will be addressed in a separate document.

The analyses of the basophil activation and skin biopsy substudy will be addressed in a separate document.

4.9 INTERIM ANALYSES

No interim analysis is planned.

For Study C, a primary database lock will be performed when all randomized participants in this study have completed their 24-week treatment phase. Analysis will be based on all data collected up to this database lock and will be considered as the final analyses in the Study C CSR.

The database will be updated at the end of the study for all participants to include the post-treatment follow-up information and updates for the events previously ongoing at the time of the primary lock. Additional data between this database lock and last participant completing last visit will be summarized in a CSR addendum.

5 SUPPORTING DOCUMENTATION

5.1 APPENDIX 1 LIST OF ABBREVIATIONS

| | |
|-------------|---|
| AAS7: | angioedema activity score over 7 days |
| ADA: | anti-drug antibody |
| AE: | adverse event |
| AESIs: | adverse events of special interest |
| ALT: | alanine aminotransferase |
| ANCOVA: | analysis of covariance, analysis of covariance |
| AST: | aspartate aminotransferase |
| ATC: | anatomic category |
| CDG: | customized drug grouping |
| CDLQI: | Children's Dermatology Life Qualtiy Index |
| CI: | confidence interval, confidence interval |
| CLcr: | creatinine clearance |
| CU-Q2oL: | chronic urticaria quality of life questionnaire |
| DLQI: | Dermatology Life Quality Index |
| DNA: | deoxyribonucleic acid |
| ECG: | electrocardiogram |
| eCRF: | electronic case report form |
| EOT: | end of treatment |
| EQ-5D-5L: | 5-level EuroQol 5-dimensional questionnaire |
| EQ-5D-Y 5L: | EuroQol 5-dimensional questionnaire youth |
| HBc Ab: | hepatitis B core antibody |
| HBs Ab: | hepatitis B surface antibody |
| HBs Ag: | hepatitis B surface antigen |
| HBV: | hepatitis B virus |
| HCV Ab: | hepatitis C virus antibodies |
| HLGT: | high level group term |
| HLT: | high level term |
| HRQoL: | health-related quality-of-life |
| HSS7: | weekly hives severity score |
| IMP: | investigational medicinal product |
| IRT: | interactive response technology |
| ITT: | intent-to-treat |
| LLT: | lower-level term |
| LS: | least squares, least squares |
| MCMC: | Markov Chain Monte Carlo |
| MedDRA: | medical dictionary for regulatory activities |
| MID: | minimal important difference |
| OCS: | oral corticosteroids |
| PCSA: | potentially clinically significant abnormality |
| PGIC: | Patient Global Impression of Change |

| | |
|---------|---|
| PGIS: | Patient Global Impression of Severity |
| PK: | pharmacokinetic |
| PT: | preferred term |
| RNA: | ribonucleic acid |
| SAE: | serious adverse event |
| SAP: | statistical analysis plan |
| SDG: | standardized drug grouping |
| SDGs: | Standardized drug groupings |
| SMQ: | standardized MedDRA query |
| SOC: | system organ class |
| TEAE: | treatment-emergent adverse event |
| UCT: | urticaria control test |
| ULN: | upper limit of normal |
| WHO-DD: | World Health Organization-Drug Dictionary |
| WOCF: | worst-observation carried forward |

